## 7.2 Analysis of Primary Outcome

The primary outcome for the study is a post-enrollment (2-week) modified Vesikari Score (MVS), defined as  $MVS \geq 9$ . The scientific hypotheses regarding the primary outcome are described in Section 3.3.

The post-enrollment score is calculated based on the elements of the score collected Day 1 through Day 14, or when symptoms resolve. Resolution of symptoms is defined as the first

Points	0	1	2	3
Diarrhea duration	0	1–96 hrs	97–120 hrs	≥ 121 hrs
Max # of diarrheal stools/24 hrs	0	1–3	4–5	≥ 6
Vomiting duration	0	1–24 hrs	25–48 hrs	≥ 49 hrs
Max # of vomiting episodes/24 hrs	0	1	2–4	≥ 5
Max recorded fever	≤ 37°C	37.1–38.4°C	38.5–38.9°C	≥ 39°C
Unscheduled healthcare visit	0	—	Primary Care	Emergency Department
Treatment	None	Rehydration	Hospital Admission	—

Table 1: Modified Vesikari Score

daily survey with absence of both diarrhea and vomiting. Each of the seven components will be assigned a score for the entire study period (from randomization to day 14). Scoring of each component is described in Table 1.

The components will be calculated by the following rules:

- 1. Maximum number of episodes of vomiting in a 24-hour period.** The number of episodes of vomiting is not collected precisely in 24-hour blocks. However, this component will be defined as the maximum number of vomiting episodes reported on a single daily follow-up survey.
- 2. Maximum number of episodes of diarrhea in a 24-hour period.** This will use the same procedure as the previous component.
- 3. Maximum temperature.** This will also use the same procedure as the two above.
- 4. Diarrhea duration.** This is calculated as the time between randomization and the last diarrhea episode. When diarrhea is reported to have stopped on one survey, and started again on a later survey, but prior to all symptoms (i.e., vomiting in this case) stopping, the durations of diarrhea episodes are summed. The first diarrhea episode would be calculated from randomization date/time until the first diarrhea stop date/time. Subsequent episodes would be calculated from the beginning (noon) of the survey day on which diarrhea reportedly returned until the next diarrhea stop date/time. In cases where diarrhea stop date/times are not in sync with the expected survey dates, we assume the date/times to be correct as long as a daily duration is no more than 84 hours (i.e., more than 3.5 days) late. Otherwise, we assume the dates are erroneous, and use the expected dates instead of the reported dates. For example, if the stop date on survey 5 should be Jan 5, but is reportedly Feb 5, we would use Jan 5. If the reported date was Jan 8, we would assume that some surveys were skipped, and

use Jan 8. If any duration is less than 0, we use 0 hours. This will happen if diarrhea stops at any time prior to randomization.

5. **Vomiting duration.** This component will be calculated using exactly the same procedure described for diarrhea when vomiting is present at randomization. If vomiting is not present at randomization and never occurs, vomiting duration will be 0. If vomiting starts after randomization, the start time will be the start time (noon) of the first daily survey where vomiting is present.
6. **Unscheduled healthcare visit.** Presence of an unscheduled healthcare visit will be collected on the survey and will be classified as “none”, “primary care”, or “emergency department”.
7. **Treatment.** Treatment will be classified as “none”, “rehydration”, or “hospital admission”. If the patient is admitted directly following their enrollment ED visit and that admission stay is longer than 48 hours, it will be counted as treatment in the post enrollment MVS. If the patient’s enrollment admission stay was less than 48 hours, it will not be counted as “treatment”. The same logic will be used for “rehydration” during the enrollment ED visit (and admission stay, if admitted).

This outcome will be tabulated by treatment for each stratum (clinical center and duration of symptoms). A Mantel-Haenszel statistic, assessing the effect of treatment on the primary outcome controlling for strata, will be calculated to test the primary hypothesis. Summary statistics for the effect sizes will be given. For dichotomous outcomes, Mantel-Haenszel risk ratios will be reported to the DSMB at interim analyses. Choice of final summary statistic reported (e.g., risk difference, risk ratio, or odds ratio) will be based, in part, by which statistic is least variable across subgroups (i.e., shows the smallest degree of interaction across subgroups).

It is expected that, for both the final analyses as well as interim analyses, the asymptotic version of the Mantel-Haenszel test will be appropriate. This analysis will be performed using SAS PROC FREQ. In the case of low outcome counts, which may occur within strata at early interim analyses, the Mantel-Fleiss criterion will be assessed. If the criterion has a value less than 5, the exact version of the Mantel-Haenszel test will be used and the two-sided p-value will be defined as the sum of all probabilities of test statistics with point probabilities less than or equal to that of the observed value.

In the event any patients were randomized within an incorrect stratum (i.e., wrong duration of symptoms) due to misspecification at time of randomization, the actual rather than assigned category will be used in the above analysis.

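### The SAP's date check repairs stop dates that are too late, but a stop date wrongly entered before its episode began is scored as 0 hours even when surveys report the symptom

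*Combined protocol and SAP*

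**What the plan says.** SAP V1.2, section 7.2, item 4 builds diarrhea duration as a sum over episodes. For the first episode: "The first diarrhea episode would be calculated from randomization date/time until the first diarrhea stop date/time". For later ones: "Subsequent episodes would be calculated from the beginning (noon) of the survey day on which diarrhea reportedly returned until the next diarrhea stop date/time".

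For stop dates that do not fit the survey schedule, the rule is: "we assume the date/times to be correct as long as a daily duration is no more than 84 hours (i.e., more than 3.5 days) late". The words in brackets run the wrong way, but the SAP's two examples settle the meaning. Beyond the limit: "Otherwise, we assume the dates are erroneous, and use the expected dates instead of the reported dates". The first example is a replaced date: "if the stop date on survey 5 should be Jan 5, but is reportedly Feb 5, we would use Jan 5". In the second, "If the reported date was Jan 8, we would assume that some surveys were skipped, and" the reported date is kept.

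Negative results have their own rule: "If any duration is less than 0, we use 0 hours. This will happen if diarrhea stops at any time prior to randomization".

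Item 5 extends this to vomiting: "This component will be calculated using exactly the same procedure described for diarrhea when vomiting is present at randomization".

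Two neighbouring provisions matter. Items 1 and 2 take the vomiting and stool counts from the daily surveys, not from the stop dates. Sections 5.4 and 7.3.1 test both durations again as secondary outcomes within the six-outcome Holm procedure.

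**The concern.** The rule exists to handle wrong dates, so it presumes that some survive into the analysis data. Yet it tests them in one direction only. An early date is never late, so it is always accepted. If it falls before the start of its episode (randomization, or noon of the survey day on which the symptom returned), the computed duration is negative and becomes 0. The only reason the SAP gives is that the symptom stopped before randomization. Nothing compares that reason with what the surveys in the same episode report.

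The derived record can then contradict itself: a child may score for stool frequency on post-randomization surveys and score 0 for diarrhea duration. At stake are two of the seven items of the primary outcome and two of the secondary outcomes.

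**Working it through.** **Inputs.** The date rules and examples are from SAP V1.2, section 7.2, items 4 and 5. The point bands are from Table 1 of that section: diarrhea 1–96 h = 1, 97–120 h = 2, 121 h or more = 3; vomiting 1–24 h = 1, 25–48 h = 2, 49 h or more = 3. The design figures are from section 3.3: 25% versus 15%, two-sided 0.05, 90% power, 670 children.

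**Rule as written.** Stop used = expected date if (reported − expected) > 84 h, otherwise the reported date. Duration = max(0, stop used − episode start).

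**Assumptions for the example.** One episode, randomization at noon on January 1, all stop times at noon.

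**Step 1, the SAP's own figures.** 84/24 = 3.5 days, as stated. February 5 for January 5 is 31 × 24 = 744 h late, so January 5 is used: 4 × 24 = 96 h. January 8 is 3 × 24 = 72 h late, so it is kept: 7 × 24 = 168 h. Both examples follow the rule.

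**Step 2, the same error reversed.** December 5 for January 5 is 744 h early. It is not more than 84 h late, so it is accepted. From January 1 back to December 5 is 27 × 24 = 648 h, so the duration is −648 h and is set to 0.

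| Expected stop | Entered as | Hours under the SAP | Diarrhea points | Vomiting points | Hours at expected date | Diarrhea points | Vomiting points |
|---|---|---|---|---|---|---|---|
| Jan 5 | Feb 5 | 96 | 1 | 3 | 96 | 1 | 3 |
| Jan 5 | Dec 5 | 0 | 0 | 0 | 96 | 1 | 3 |
| Jan 6 | Dec 6 | 0 | 0 | 0 | 120 | 2 | 3 |
| Jan 7 | Dec 7 | 0 | 0 | 0 | 144 | 3 | 3 |

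**Step 3, where zeroing stops.** Early dates that still fall after the episode start are not zeroed. With January 5 expected, January 3 gives 48 h and January 2 gives 24 h.

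**Step 4, effect on the cut-off.** A zeroed single-episode item loses k = 1 to 3 points, so a child with a true score from 9 to 8 + k becomes a non-event. For k = 3 that is 9 to 11. If both duration items are hit, the loss can reach 6. In a summed duration only the zeroed episode's hours are lost.

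**Step 5, effect on power (illustration).** The usual two-proportion formula without continuity correction gives 335 per arm, which reproduces 670. Let a share q of true events fall below 9 in both arms, so the rates are 0.25(1 − q) and 0.15(1 − q).

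| q (assumed) | Rates | Difference, points | Power at 335 per arm |
|---|---|---|---|
| 0 | 25.00% vs 15.00% | 10.0 | 90.1% |
| 1% | 24.75% vs 14.85% | 9.9 | 89.7% |
| 2% | 24.50% vs 14.70% | 9.8 | 89.3% |
| 5% | 23.75% vs 14.25% | 9.5 | 88.2% |

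Here q counts only true events that are misdated to before the episode start, survive data cleaning and then drop below 9. It is smaller than the share of children with any wrong date.

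**The case against.** The zero rule has a proper purpose. A child whose diarrhea ended before randomization has no post-randomization diarrhea, and 0 hours is then correct. This stands, and any fix must keep it.

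Other controls may catch the errors. Section 5.2 has outliers reviewed, section 6.4 requires significant queries to be resolved before the final analysis, and section 5.6 leaves derivation detail to dataset specifications. Neither those specifications nor the case report forms are among the documents, so an entry check may already block a stop date before randomization. This stands in part: the controls are general and none is tied to this rule. Three others do not help. Multiple imputation (section 7.2.1) acts only when missing data prevent derivation, and a forced 0 counts as observed. The sensitivity analysis in section 7.2.3 removes children with surveys collected late, not those with wrong dates. Dual programming reproduces a gap in a specification that both programmers follow.

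A reader might infer that every early date is zeroed, or that the child's illness disappears from the score. The text does not support either. Only a stop before its episode's start is zeroed, and counts, temperature, visits and treatment still score. Nor is the net effect of all date errors one-sided: wrong dates up to 84 h late are accepted and lengthen durations.

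A mirrored 84-hour limit for early dates may look like the natural remedy, but it is not safe. Protocol V3.0, section 3.4 lets missed days be collected at a later contact, so an early stop date after the episode start can be genuine.

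**Conclusion.** The gap is real on the text of SAP V1.2: the wrong-month error that the SAP repairs when late is scored as 0 hours when early, if the date then precedes the episode start. Each affected duration item can lose 1 to 3 points, and the matching secondary duration is shortened. The same holds for vomiting present at randomization.

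The size in practice is unknown, because the documents give no error rate and do not show that any such date reached the analysis data. With 0 to 5% of true events lost, an assumed range, power moves from 90.1% to 88.2%. A reader might go further and infer a bias for or against the probiotic. Nothing in the documents suggests that these errors differ between blinded arms, so slight dilution is the likely result. Severity: minor.

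**What to change.** Add a check to section 7.2, item 4, made episode by episode and carried over to item 5:

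- If an episode's computed duration is negative and a survey belonging to that episode reports the symptom after randomization, treat the stop date as erroneous. Use the expected date of the last survey in that episode that reports the symptom, with the same handling as for late dates.
- If no post-randomization survey in that episode reports the symptom, keep 0 hours.
- Leave early dates that fall after the episode start as reported.

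Working per episode matters because durations are summed. A child whose diarrhea truly stopped before randomization and returned while vomiting continued should get 0 hours for the first episode plus the hours of the later one. A condition on the whole child would add hours to the first episode that did not occur.

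The cost is a sentence or two in the SAP and a few lines of derivation code. The rule can be written without reference to treatment arm.

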### 5.1 Specific Aim Analyses

**Specific Aim 1.** Determine the clinical effectiveness of probiotic administration to reduce morbidity in children presenting to the emergency department with acute

gastroenteritis.

The **primary efficacy endpoint** of this study is the presence of moderate-severe acute gastroenteritis, as defined by a total post-enrollment Modified Vesikari Score  $\geq 9$  during the 2-week follow-up period. Each of the 7 items in the score is tabulated individually (maximum of 20 points); the sum of these individual variables represents the total Modified Vesikari Score. At the time of randomization a baseline Modified Vesikari Score will be assigned based on symptoms prior to randomization. This baseline score will serve as a covariate in a secondary analysis of the primary outcome. The post-enrollment Modified Vesikari Score which will be employed to determine the presence/absence of the primary efficacy outcome, is based only on symptoms that occur between randomization and day 14, the conclusion of the study period for this outcome. Only symptoms and outcomes that occur following randomization will be included in the post-enrollment score.

The post-enrollment score is calculated only once, on day 14. At that time, each of the seven variables will be assigned a score for the entire study period (from randomization to day 14). Each variable will be scored by 1 of 3 methods:

1. Worst 24 hour period - maximal number of episodes of vomiting in a 24 hour period, maximal number of episodes of diarrhea in a 24 hour period, and maximal temperature;
2. Total duration of symptoms, including the number of days on which any gastroenteritis-related symptom occurred;
3. Occurrence of a treatment outcome or unscheduled subsequent healthcare utilization. If the patient was admitted directly following their enrollment ED visit and that admission stay is longer than 48 hours, it will be included as treatment in the post enrollment MVS. If the patient's admission stay was less than 48 hours, it will not be included in any MVS calculation.

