### 3.3 Sample Size and Power Determination

The primary outcome is binary: whether total post-enrollment Modified Vesikari Score (MVS) is  $\geq 9$  during the 2-week follow-up period. The difference between arms will be tested at a 0.05 level. The null and alternative hypotheses are, respectively,

$$H_0 : p_A = p_P \quad \text{and} \quad H_1 : p_A \neq p_P,$$

where  $p_A$  and  $p_P$  are, respectively, the true probabilities of  $MVS \geq 9$  on the Active drug and on Placebo.

Our pilot data indicate that 25% of patients will have moderate to severe disease ( $MVS \geq 9$ ) during the course of their illness. Furthermore, expert surveys indicated that an absolute risk reduction of 10% would constitute a minimal clinically-important difference (MCID). Therefore, our sample size calculation assumed a 25% event rate in the control group for which we desire to detect an absolute beneficial treatment effect of 10% with 90% power (0.1 Type II error rate). Using a two-sided type I error ( $\alpha$ ) of 0.05 and the hypothesized proportions yields a required total sample size of 670 patients. Our expected power, should we find different event rates in our 2 groups, is displayed in the following table.

Placebo	Active	% Difference	Power
0.30	0.21	9%	0.76
0.30	0.20	10%	0.85
0.25	0.15	10%	0.90
0.25	0.16	9%	0.82
0.25	0.17	8%	0.72
0.20	0.10	10%	0.95
0.20	0.12	8%	0.81
0.20	0.13	7%	0.69

Based on previous work by our group, we assumed 10% loss to follow-up ( $670/0.90 = 744$ ), 5% drop-out, and 3% drop-in (caregivers who buy a probiotic agent to administer to their child) rate ( $744/(0.92)^2 = 879$ ). Adjustment for O’Brien-Fleming monitoring boundaries requires a further 2% increase. Thus, the total number randomized (final target sample size) will be 900.

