### 6.2 Stopping Rules for Interim Analyses

Two-sided O'Brien-Fleming boundaries, implemented using the alpha-spending function approach will be used. Specifically, if the analyses are performed exactly when planned, the significance levels that will be used at interim analyses are 0.00065 and 0.0136. If the trial reaches the anticipated total sample size, a significance level of 0.0457 will be used for the final test. These boundaries assure that the total Type I error rate will be less than or equal to 0.05.

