### 7.2.2 Additional Analyses of Primary Outcome

A secondary analysis of the primary outcome will test for treatment effect on the primary outcome using a logistic regression model with baseline MVS as a covariate. We will also analyze the MVS outcome as a continuous variable. For this analysis, treatment groups will be compared using a Van Elteren test, stratified by center and duration of symptoms.

We will perform further analyses of the MVS score outcomes by assessing the treatment effect after adjustment for covariates. The covariates that will be included have been described previously. A logistic regression model will be used for the indicator outcome of moderate-severe disease ( $MVS \geq 9$ ). Linear models will be used for the continuous MVS score. These models will be evaluated and adjustments will be made if any assumptions appear to be seriously violated. For example, a distribution other than the normal distribution may be used for the MVS score.

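### The primary Mantel-Haenszel test is valid and powered as stated, but it leaves the precision available from baseline MVS unused

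*Combined protocol and SAP*

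**What the plan says.** SAP 7.2 tabulates the primary outcome by treatment within strata of clinical center and symptom duration (under 48 hours versus 48 hours or more). It tests the hypothesis with a Mantel-Haenszel statistic "assessing the effect of treatment on the primary outcome controlling for strata". Protocol 5.1 names the same two stratification factors.

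Protocol 5.1 also has a baseline MVS assigned at randomization from symptoms up to that point, and fixes its role: "This baseline score will serve as a covariate in a secondary analysis of the primary outcome". SAP 7.2.2 follows with a secondary test "using a logistic regression model with baseline MVS as a covariate", and then with further models that carry the covariate list of SAP 2.3. Baseline MVS stands first in that list, which is introduced as concerning baseline variables important for the outcomes; the list's adjusted analyses are described as exploratory. SAP 7.2.1 admits individual baseline score items as candidate predictors for imputation. Through that route they can reach the primary test only for children with partly missing outcomes.

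The sample size in SAP 3.3 takes no credit for any covariate: "our sample size calculation assumed a 25% event rate in the control group" and "we desire to detect an absolute beneficial treatment effect of 10% with 90% power".

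**The concern.** The outcome is a cut of a severity score, and the same instrument is scored at baseline. The plan itself treats that baseline value as prognostic, yet randomization is not stratified by it and the primary test does not condition on it. If the score predicts the outcome beyond center and symptom duration, the primary comparison has a larger standard error than it needs, and chance differences in baseline severity stay in it as noise.

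What is at stake is power and interval width. The design effect has little slack to gain, but effects below 10 points have more: SAP 3.3 puts power at only 0.72 for 25% versus 17%. Any gain would need no further children.

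**Working it through.** **Inputs.** All are from SAP 3.3 unless noted.
- Test level: "The difference between arms will be tested at a 0.05 level"; sidedness: "Using a two-sided type I error".
- Control rate 25%, active rate 15%, target power 90%, equal allocation (SAP 3.1).
- Stated evaluable total: 670.
- Final look (SAP 6.2): "a significance level of 0.0457 will be used for the final test".
- Share of outcome variance that baseline MVS explains beyond center and duration stratum (added R²): **not in the documents**, so it is an assumption, varied from 0 to 0.20.

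**Step 1: reproduce the plan's figure.** Pooled-variance two-proportion formula without continuity correction, per arm:

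n = [z₀.₉₇₅ √(2p̄q̄) + z₀.₉₀ √(p₁q₁ + p₂q₂)]² / d²

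With p̄ = 0.20, √(2 × 0.20 × 0.80) = 0.5657. Also √(0.25 × 0.75 + 0.15 × 0.85) = √0.315 = 0.5612. So n = (1.960 × 0.5657 + 1.2816 × 0.5612)² / 0.10² ≈ 334.2, rounded up to 335 per arm, or **670**. This matches the plan. The inflation steps also reproduce: 670/0.90 = 744; 744/0.92² = 879; 879 × 1.02 = 897. All eight rows of the power table reproduce at 335 per arm. At the final-look level of 0.0457, 670 children give 89.4%, which the plan's 2% increase covers. The stated power therefore does not depend on baseline MVS.

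**Step 2: allow for the covariate.** Adjustment multiplies the residual variance by about (1 − R²), so the effective n per arm is 335/(1 − R²). Power is Φ{[d√n − 1.960√(2p̄q̄)] / √(p₁q₁ + p₂q₂)}. For example, at R² = 0.10, n = 372.2 and (0.10 × 19.293 − 1.1087)/0.5612 = 1.462, so power is 92.8%. The last column is 2 × 335 × (1 − R²), with each arm rounded up.

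| Added R² | Effective n per arm | Fall in SE | Power, 25% vs 15% | Power, 25% vs 17% | Evaluable total for 90% (25% vs 15%) |
|---|---|---|---|---|---|
| 0 | 335 | 0 | 90.1% | 72.1% | 670 |
| 0.02 | 341.8 | 1.0% | 90.6% | 72.9% | 658 |
| 0.05 | 352.6 | 2.5% | 91.5% | 74.3% | 638 |
| 0.10 | 372.2 | 5.1% | 92.8% | 76.5% | 604 |
| 0.20 | 418.8 | 10.6% | 95.3% | 81.2% | 536 |

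**Step 3: check by simulation against the planned test.** Assumptions: 670 children, 10 centers by 2 duration strata, a normally distributed baseline score positively correlated with the duration stratum, 3,000 runs per scenario, nominal 0.05. The stratified Mantel-Haenszel test was compared with logistic regression on center, duration and score.
- 25% vs 15%: 90.4% vs 90.4% when the score has no prognostic value; 90.5% vs 92.2% at R² about 0.08; 90.3% vs 93.6% at about 0.15; 90.0% vs 95.1% at about 0.22.
- 25% vs 17% at R² about 0.15: 73.7% vs 79.3%.
- No treatment effect: rejection rates of 5% to 6% for both tests.

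Two cautions apply. R² here is the whole share explained by the score, part of which the duration stratum already holds, so it slightly overstates the added R² of step 2. The simulated logistic test was also a Wald test of the conditional odds ratio; the standardized risk difference proposed below was not itself simulated.

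**The case against.** The strongest reply is that nothing here is defective. The Mantel-Haenszel test conditions on exactly the randomization factors, is valid, has an exact fallback for sparse data, and delivers its stated power. That stands.

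The gain may also be small. Baseline MVS is not simply the outcome measured earlier: the post-enrollment score counts only what follows randomization, and one item concerns later unscheduled visits. The baseline score gives more points for longer illness, whereas the simulations in SAP 4.3 assume a lower untreated event rate with longer symptoms (20% beyond 2 days, 30% otherwise). Duration points could therefore work against frequency and fever points. The primary test also already holds part of the duration information. All of this stands: the added R² is unknown and could be near zero.

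A reader might infer that an unadjusted and an adjusted result leave it open which one is primary. The documents do not support that. SAP 7.2 and 7.2.1 name Mantel-Haenszel as the test of the primary hypothesis, and protocol 5.1 and SAP 7.2.2 label the baseline-MVS model secondary. A reader might also infer that the model needed is already planned. It is not: one model in SAP 7.2.2 names baseline MVS alone and the other carries the whole covariate list.

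Finally, a late change of primary test has a cost. The interim, enrichment and imputation rules are written for Mantel-Haenszel, and SAP 6.3 lets data center statisticians see results by arm A and B. That limits who may decide and how the change is made, but does not remove the case for it.

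**Conclusion.** The point holds as one of efficiency. The planned primary test is sound; it does not use a prognostic baseline value that the plan intends to collect on every child. At 670 evaluable children and the design effect, the gain is zero if the score adds nothing beyond the strata, and about 1.4, 2.7 and 5.2 points of power at added R² of 0.05, 0.10 and 0.20. For 25% versus 17% the gains are about 2.2, 4.4 and 9.1 points. In simulation, adjustment cost no power when the score was uninformative, and type I error was similar. The size rests wholly on an assumed R². The figures do not support reading this as an underpowered or biased primary analysis.

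**What to change.** - **Primary analysis.** Prespecify a logistic model with center, symptom-duration stratum and continuous baseline MVS, as a modification of the models in SAP 7.2.2. Test and report the standardized risk difference with its own standard error. Test and estimate then agree, on the absolute scale of the 10-point target.
- **Interim and enrichment.** Use the same z against the SAP 6.2 boundaries and in the enrichment and stage-combination rules of SAP 4.3, taking that section's weights as given here. Within a duration subpopulation the duration term drops out.
- **Imputation.** Pool the estimate and standard error across imputed datasets, in place of the signed chi-square roots in SAP 7.2.1.
- **Gaps to fill.** State a simple rule for a missing baseline score (for example, a fill-in value computed without regard to arm) and one for sparse centers at the first efficacy look, near 350 children (for example, a fixed pooling rule).
- **Supportive analysis.** Keep the stratified Mantel-Haenszel test, in its exact version when data are sparse.
- **Who decides.** Only people who have not seen results by arm A and B. If that cannot be shown, keep Mantel-Haenszel as primary and name one adjusted analysis as the main supportive result.

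The cost is matching wording in protocol 5.1 and in SAP 4.3, 6.2, 7.2, 7.2.1 and 7.2.2, and a primary test that becomes model-based. No further children are needed.

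### SAP 7.2 lets the reported primary effect measure depend in part on observed subgroup variability, so the headline estimate and its interval are not pre-specified and may not be on the MCID's absolute scale

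*Combined protocol and SAP*

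**What the plan says.** SAP V1.2, section 7.2 (V1.1 has the same text), fixes the test: "A Mantel-Haenszel statistic, assessing the effect of treatment on the primary outcome controlling for strata, will be calculated to test the primary hypothesis". It also fixes what the monitoring board sees: "Mantel-Haenszel risk ratios will be reported to the DSMB at interim analyses". It does not fix the final estimate: "Choice of final summary statistic reported (e.g., risk difference, risk ratio, or odds ratio) will be based, in part". The only criterion that the section goes on to name is stability of the measure, that is, "which statistic is least variable across subgroups (i.e., shows the smallest degree of interaction across subgroups".

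The section does not say what else the choice rests on, which subgroups decide it, how variability is measured, or what happens in a tie. Sections 5.5 and 7.6 list three formal subgroup factors (age, prior antibiotics, infectious agent), and 5.5 adds symptom duration.

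No other section closes the gap. Protocol V3, section 5.1, names the Mantel-Haenszel test and no effect measure. SAP 7.2.1 calculates a Mantel-Haenszel odds ratio only to give the z-statistic its sign, and describes pooling only of z across imputed datasets.

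The target is absolute. SAP 3.3 says that "expert surveys indicated that an absolute risk reduction of 10% would constitute a minimal clinically-important difference", and that "our sample size calculation assumed a 25% event rate in the control group".

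**The concern.** A test and an estimate answer different questions. The test is settled in advance. The estimate and interval that readers will use to judge how large the benefit is, or how large a benefit can be ruled out, depend on a choice that needs outcome data by arm and by subgroup.

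Two things are at stake. First, the trial is sized for the main effect, not for interactions, so apparent differences in stability between the three scales may be mostly chance. Second, two of the three named candidates are relative measures, while the trial's question, minimal important difference and sample size are all absolute. This matters most if the result is null, because protocol section 1 says resources would then be redirected. Readers would want to know whether a 10-point benefit is excluded.

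**Working it through.** **1. The plan's own sample size.** Inputs from SAP 3.3: 25% versus 15%, two-sided alpha 0.05, power 90%; equal allocation from SAP 3.1. With the pooled-variance formula without continuity correction, the mean rate is 0.20 and

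n per arm = [1.96 × √(2 × 0.20 × 0.80) + 1.2816 × √(0.25 × 0.75 + 0.15 × 0.85)]² / 0.10² = (1.109 + 0.719)² / 0.01 ≈ 334.2.

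Rounded up, this is 335 per arm and 670 in total, as stated. All eight rows of the power table reproduce within 0.01. The plan is built on the risk difference.

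**2. The design effect on each scale.**
- Risk difference: 0.25 − 0.15 = 10 points
- Risk ratio: 0.15 / 0.25 = 0.60
- Odds ratio: (0.15 / 0.85) / (0.25 / 0.75) = 0.529

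**3. What a relative measure implies in absolute terms.** The control rates are those in the SAP 3.3 power table.

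| Control rate | Reduction if RR = 0.60 | Reduction if OR = 0.529 |
|---|---|---|
| 20% | 8 points | 8.3 points |
| 25% | 10 points | 10.0 points |
| 30% | 12 points | 11.5 points |

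A risk ratio or odds ratio therefore shows whether the 10-point threshold is met only when it is read with a control rate.

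**4. How the selection rule behaves.** SAP 7.2 gives no metric, so this is an illustration under stated assumptions:
- one factor with two equal subgroups and placebo rates of 30% and 20% (the simulation assumptions in SAP 4.3, where the factor is symptom duration);
- 900 children, in four equal cells of 225;
- for each scale, Q = (e₁ − e₂)² / (v₁ + v₂), where e is the subgroup effect (risk difference, log risk ratio or log odds ratio) and v its variance, with 0.5 added to each count;
- the scale with the smallest Q is chosen;
- 40,000 simulated trials per scenario.

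| Truth | RD chosen | RR chosen | OR chosen |
|---|---|---|---|
| Constant RD, 10 points | 65% | 19% | 16% |
| Constant RR, 0.60 | 32% | 53% | 14% |
| Constant OR, 0.529 | 38% | 47% | 16% |
| No effect | 49% | 48% | 3% |

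When the risk difference is truly constant at 10 points, another scale wins about 35% of the time. For smaller constant differences that figure rises, to about 39% at 8 points and 45% at 5 points. The results barely move with sample size: at 670 and 970 children the risk difference is chosen 63% and 65% of the time under a constant 10-point difference. Using 970 less 10% loss (970 × 0.90 = 873) gives the same 35% and, at 8 and 5 points, 39% and 45%.

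**5. Can the data tell the scales apart?** At 900 children and a constant 10-point risk difference, a 5% heterogeneity test rejects 5% of the time on the true scale, 15% on the risk ratio and 11% on the odds ratio. The evidence separating the scales is weak.

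**6. What does not move.** The p-value comes from the Mantel-Haenszel test whichever summary is reported. The 670 before inflation, alpha and power are the same under any choice.

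**The case against.** The strongest reply is that looking for a measure that is stable across subgroups is a recognised idea, and that the absolute answer is never lost. SAP 7.2 tabulates the outcome by arm within each stratum, so anyone can compute a risk difference. The conversion is close: simulated with a 10-point effect, turning a pooled Mantel-Haenszel odds ratio into a risk difference at the observed placebo rate lands within about 0.13 points of the risk difference on average, and within about 0.3 points in 97.5% of trials. This stands. A point estimate judged against 10 points would rarely change sides. What is missing is mainly a pre-stated confidence interval on that scale.

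Several stronger readings are tempting and should be resisted.
- *The measure is chosen after unblinding.* SAP 6.3 has the statisticians seeing arms as A and B without their identity, and heterogeneity can be assessed that way. What the text supports is that outcomes by arm must have been seen.
- *Subgroup stability is the only criterion.* The SAP says it is part of the basis. The rest is unstated and could include the MCID, so the risk difference may still be chosen. The simulation treats the criterion as decisive, which is a simplification.
- *The rule conceals heterogeneity.* SAP 7.6 reports primary outcome rates by arm in every prespecified subgroup and tests interaction in a logistic model at 0.017, whichever summary is headlined.

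The selection percentages also count how often the reported scale changes. They do not measure how often a reader would reach a wrong conclusion.

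**Conclusion.** The concern holds as a matter of estimation and reporting. SAP 7.2 lets the final effect measure depend in part on comparative outcome data, and nothing elsewhere fixes it. The headline estimate and interval are therefore not pre-specified and may be on a scale other than that of the 10-point MCID.

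Under the working's assumptions, a truly homogeneous 10-point risk difference would still be passed over about 35% of the time, and a truly homogeneous odds ratio of 0.529 would be picked only about 16% of the time. Those figures rest on an assumed metric, one assumed two-level factor and subgroup stability deciding alone. The conclusion that the choice is largely noise does not depend on their exact values.

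A reader might infer that the primary test is compromised. The documents do not support that: the test is fixed, and type I error and power are intact. This should be corrected, but it does not threaten the trial's validity.

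**What to change.** In SAP 7.2, state that the primary estimate is the stratified Mantel-Haenszel risk difference (clinical center and symptom duration) with its confidence interval, and that the risk ratio and odds ratio are supportive and will be reported whatever the subgroup results. Delete the sentence that makes the choice depend on variability across subgroups. Because SAP 7.2.1 describes combining only z across imputed datasets, add there that the risk difference and its standard error are combined as well. Make the change before outcomes by arm are used to choose a measure; if any have already been reviewed, record that with the amendment.

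The cost is one or two sentences. Sample size, alpha, power, the interim risk ratios for the monitoring board and the subgroup analyses in 7.6 stay as they are.
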